### **Fruit/Vegetable Consumption (Heart Healthy Diet): I-FV**

For the second arm of this study, we will use a culturally-tailored program developed specifically for the American Indian population to reduce their risk of heart disease, "*Honoring the Gift of Heart Health.*" We will obtain copyright permission and modify the materials used in this program by removing the information related to smoking cessation for one of their sessions. These sessions help American Indians learn about what they can do to prevent heart disease. We will emphasize the increase consumption of fruits and vegetables as well as addressing other heart healthy activities. *Honoring the Gift of Heart Health* is a user-friendly program developed especially for American Indians. The manual provides the "how-to" for leading group education

sessions. It offers "hands-on" activities that help people build the skills they need to make simple, practical, and lasting changes to help them fight heart disease. The protocol will follow procedures as the I-ANBL arm, however, this fruit and vegetable arm will not include individually tailored components, but just interactive web-based materials related to increasing heart health, including certain activities.

## Measures

**Schedule of Assessments:** The table below represents our preliminary listing of outcome assessments, based on measures used for ANBL and preliminary discussions with community members. During year one of the project, we will work closely with our community partners to refine all measures and potentially add or subtract some of them. Our community partners will have final say on all measures to be used, including whether we use standard measures validated in other populations or modify for our community.

Measures Week	1	2	3	4	5	6	7	8	12	6 mo
Primary Outcome										
The primary endpoint for the study will be biochemically (salivary cotinine) verified point prevalence abstinence, defined as no smoking for the previous 7 days, at the 6-month follow-up. This definition is based on recent consensus statements from the Society for Research on Nicotine and Tobacco Subcommittee on Abstinence Measures.	X								X	X
Biochemical Validation	X								X	X
Pharmacotherapy Use		X	X	X	X	X	X	X	X	
Demographics Tribal affiliation, age, gender, marital status, income, year in school	X									
Smoking behavior										
Traditional use of tobacco	X	X	X	X	X	X	X	X	X	X
Smoking history (age of initiation)	X									
Quitting history (length of most recent quit attempt, number of quit attempts in the past year)	X									
Self-reported Smoking status (number of cigarettes/day)	X	X	X	X	X	X	X	X	X	X
Nicotine Dependence - The Fagerstrom Test of Nicotine Dependence will be used to measure nicotine dependence. 	X								X	X
Self-efficacy	X			X				X	X	X
Motivation	X			X				X	X	X
Environmental factors										
Household structure	X								X	X
Social support	X								X	X

Exposure to others who use tobacco in any form	X			X		X			X	X
Exposure to tobacco marketing	X			X		X			X	X
Psychosocial factors										
Depression using the CES-D, 10-item. 	X		X		X		X		X	X
Negative Affect from the Positive and Negative Affect Scale (PANAS) , 	X		X		X		X		X	X
Nicotine Withdrawal using the Minnesota Withdrawal Scale (MNWS) 	X		X		X		X		X	X
Craving using the Brief Questionnaire of Smoking Urges (QSU-Brief) , 	X		X		X		X			
Treatment Factors										
Satisfaction with interactive website					X				X	X
Satisfaction with session topics		X	X	X	X	X	X	X	X	
Satisfaction with session educational materials	X	X	X	X	X	X	X	X	X	
Satisfaction with cultural appropriateness of program	X	X	X	X	X	X	X	X	X	
Frequency of usage of website	X	X	X	X	X	X	X	X	X	X
Consumption of Fruits	X		X		X		X		X	X
Consumption of Vegetables	X		X		X		X		X	X

**Process Measures and Evaluation:** We plan a detailed process evaluation, with two primary methods, individual surveys after each internet session and surveys after the close of the study. Individual session surveys will focus on content and cultural appropriateness of the session and will include 5-point Likert scale questions and open-ended questions to provide both a quantitative measure of the sessions for comparison among sessions and a qualitative measure for depth of understanding. After the 6-month follow-up, participants will be surveyed individually through the website regarding program exposure and dose: how much of the curriculum materials they used, and how much, if any, pharmacotherapy was used. Participants will also be asked to rate program components overall on a five-point Likert scale for perceived helpfulness, satisfaction, and cultural attentiveness/sensitivity. To assess acceptability, the question commonly used is, “Would you recommend this intervention/program to another friend/relative etc. who smokes?” We will also collect information related to the indicators of feasibility including monthly recruitment rates, retention rates, and frequency of use.

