**Anticipated Flow of Participants:**

Telephone Eligibility Screening Interview		
↓		
In-Person Randomization Visit (n=300)		
←      ↓      →		
Web-based weekly		
Sessions	I – ANBL (n=150)	I – FV (n=150)
1	Preparing to quit, pharmacotherapy/nrt, why do people smoke	Assessment of Risk for Heart Disease, pharmacotherapy/nrt
2	Cigarette smoking and Native people, Quit smoking date	Increasing fruit and vegetable consumption, Quit smoking date
3	Coping with Withdrawal	Physical activity
4	Traditional use of tobacco	High blood pressure
5	Stress reduction and relaxation techniques, traditional meditation techniques	Salt and sodium intake
6	Weight management, Healthy American Indian foods, exercise	High Cholesterol
7	Friends and family and quitting smoking, social support	Maintaining healthy weight
8	Staying quit – congratulations Long term maintenance	Low cost healthy eating – fruits and vegetables
Email reminders will be sent before each session so that participants will log in at the appropriate time		
12	End of pharmacotherapy treatment, feedback of program	End of program, feedback

Email reminders will be sent before each session so that participants will log in at the appropriate time		
Month 6	Assessment for current smoking status	Assessment of current smoking status

(Detailed descriptions of the weekly I-ANBL web materials are included in the appendix: will be adapted to integrate tribal college student issues identified during Phase 1 of the study)

- Telephone Screening Intake:** Research Assistants will review inclusion/exclusion criteria, smoking status and basic information about the program. We will not exclude participants who use other forms of recreational tobacco (eg – smokeless tobacco) because, based on our preliminary data, we would be excluding eligible participants if we did so. In addition, community members have encouraged us to be more inclusive for acceptability of the research in the community and make the inclusion criteria less restrictive. Therefore, we will examine use of other tobacco products in a secondary analysis. We estimate screening intake to take 10-15 minutes.

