- Internet Session 1:** Participants will be asked to log into the website prior to the first session to allow for any problems with the site to be fixed prior to sessions starting. Participants who decide to take any study medication will need to visit the Polson Tribal Clinic in Polson, MT to pick up a one month supply of study medication. Any unused NRT or medication will be dropped off at the clinic and then mailed back to the research assistants by the clinic staff. The study physician will be available to answer additional

questions. Beginning with this session and continuing through all sessions. Topics we anticipate covering include, but are not limited to: preparing to quit, dealing with cravings, support systems, traditional tobacco, stress reduction, weight management, and staying quit, along with other topics determined during program development. For each session, the tribal college student will begin the session by answering a series of questions to produce an individually-tailored report that will be provided on the screen at the end of each week's session so that the smoker can work on strategies during the week before the next internet session. Estimated time for the web session is 30 minutes.

- **Internet Sessions 2-8:** *The second session is the quit date for all participants in the group.* Weekly procedures will follow the same format as for the first session. At the session dealing with traditional tobacco, participants will be asked to talk about their own use, though they will not be required to do so because this is not always culturally appropriate. Participants will be asked to fill out weekly brief surveys about their use of tobacco during the week; e-mail reminders will be sent. Participants will also be asked to fill out brief session evaluations on-line after each session; e-mail reminders will be sent for these as well. Session evaluations will go directly into a separate database that will be de-identified; participants will be told about this database to encourage more truthful responses.
- **Weeks 9-11:** Participants will receive one individual email per week from a research assistant.
- **Final Session- End of Treatment (Week 12):** Session content procedures will follow the same format as for other sessions. All participants, regardless of smoking status will receive a certificate of achievement for completing the program and will be asked to submit a saliva sample.

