- **6-Month Follow-Up:** At 6-months post-baseline, participants are asked to take part in a final internet session and will receive a \$20 gift card for participation. They will be asked about their smoking status and will be asked to submit a saliva sample. Participants who do not report abstinence from smoking use will be asked if they would like to participate in the full program again. If they choose to participate a second time, they will not be included in *study outcome* measures, though we will track their success. This is done to mimic the real-world situation where a program could be repeated. After the 6-month follow-up, participants will be sent a final anonymous survey about the program via e-mail.

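### Cotinine is the only verifier of cigarette abstinence and users of other tobacco are enrolled, yet no month-6 item records participants' own use of such tobacco

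*Protocol*

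**What the plan says.** All references are to the protocol.

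- **Endpoint.** The Measures section states: "The primary endpoint for the study will be biochemically (salivary cotinine) verified point prevalence abstinence, defined as no smoking for the previous 7 days". The time point is month 6. Sample Size and Power and the Primary Aim analysis also name cotinine and no other verifier.
- **Entry.** Under Anticipated Flow of Participants, the telephone screening item reads: "We will not exclude participants who use other forms of recreational tobacco". The reasons given are the team's preliminary data and community advice. It then commits to an analysis: "Therefore, we will examine use of other tobacco products in a secondary analysis".
- **Month 6.** Of participants at the 6-month follow-up, the text says: "They will be asked about their smoking status and will be asked to submit a saliva sample".
- **Schedule of assessments.** The tobacco rows marked at 6 months are traditional use, cigarettes per day, Fagerstrom dependence, and "Exposure to others who use tobacco in any form". The last concerns other people's use. Pharmacotherapy Use is marked at weeks 2-8 and 12 and is blank at 6 months.
- **Other possible sources.** Sessions 2-8 include "weekly brief surveys about their use of tobacco during the week". After the 6-month follow-up, the process evaluation asks "how much, if any, pharmacotherapy was used", and the follow-up text says "participants will be sent a final anonymous survey about the program via e-mail".
- **Smoker definition.** Section IV leaves current smoking to the participant's own definition. Eligibility Requirements in Section V asks for at least one cigarette in the past 30 days.

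**The concern.** The outcome is about cigarettes, but the verifying test responds to nicotine from any source. Someone who has stopped cigarettes and uses smokeless tobacco will have positive cotinine and be counted as a smoker. The protocol expects such users, since it declines to exclude them on the strength of its own preliminary data.

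Two things follow. The primary comparison cannot be examined for this misclassification, because nothing scheduled at month 6 shows who is affected. And the promised secondary analysis of other tobacco has no scheduled month-6 data.

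If I-ANBL changes the use of other tobacco relative to I-FV, the difference in verified abstinence could move either way. An SAP can add analyses later, but it cannot supply an item that was not asked at month 6.

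**Working it through.** **1. Which scheduled item could show other nicotine use at month 6?**

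| Item | Marked at 6 months | Shows participant's own smokeless or other recreational tobacco? |
|---|---|---|
| Traditional use of tobacco | yes | no, traditional use only |
| Cigarettes per day | yes | no |
| Fagerstrom test | yes | no |
| Exposure to tobacco users | yes | no, other people's use |
| Pharmacotherapy Use | no | no |
| Weekly tobacco surveys | no, described for sessions 2-8 | possibly, but not at month 6 |
| Survey after month 6 | after the follow-up | no; asks about pharmacotherapy over the program, and may be the survey called anonymous |

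No row fills the gap.

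**2. The plan's own figure.** Inputs from Sample Size and Power: 30% v 15%, chi-square test, 5% type I error, 80% power. I take the test as two-sided, with pooled variance and no continuity correction:

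n = [1.96 × √(2 × 0.225 × 0.775) + 0.842 × √(0.30 × 0.70 + 0.15 × 0.85)]² / 0.15² = 120.5, so 121 per arm, with power 80.2%. The stated 121 reproduces and is not in dispute.

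**3. Illustration of misclassification.** Take 30% and 15% as the cotinine-verified rates: 121 × 0.30 = 36.3 and 121 × 0.15 = 18.15, so 36 v 18. Then add back assumed numbers of cigarette quitters who failed cotinine because of other tobacco. The test is z = (p1 − p2) / √(2p(1 − p)/121), where p is the pooled proportion.

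| Added back | Quitters, I-ANBL v I-FV | Difference | z | Two-sided p |
|---|---|---|---|---|
| none | 36 v 18 | 14.9 points | 2.78 | 0.005 |
| 5 in I-FV only | 36 v 23 | 10.7 points | 1.95 | 0.052 |
| 5 in I-ANBL only | 41 v 18 | 19.0 points | 3.44 | 0.0006 |
| 5 in each arm | 41 v 23 | 14.9 points | 2.62 | 0.009 |

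Four in I-FV only (36 v 22) gives p=0.035, so five is the smallest one-sided imbalance that crosses 5% here. The count of five is an assumption.

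**4. Secondary point: entrants already abstinent.** Under either smoker definition, a person whose last cigarette was 8-30 days ago can enrol while already meeting the self-report part of the endpoint. Let a share f of entrants be in this state, and let 70% of them be abstinent at month 6 in either arm (assumed). Each arm's rate is (1 − f) × planned rate + 0.7f. The last column leaves these entrants out, with 30% v 15% at 121(1 − f) per arm.

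| f | Rates | Power, all | Power, without them |
|---|---|---|---|
| 2% | 30.8% v 16.1% | 77% | 79% |
| 5% | 32.0% v 17.75% | 73% | 78% |
| 10% | 34.0% v 20.5% | 66% | 76% |

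With 50% to 90% in place of 70%, power with everyone included is 78-77%, 74-72% and 68-64% for the three shares. This is dilution. The added rate is the same in both arms, so under no effect the arms stay equal and type I error is not inflated.

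**The case against.** **The schedule is preliminary.** The Measures section calls it so and plans to refine it with community partners in year one, and the other-tobacco analysis is already promised. Item wording is not given, so a month-6 survey might cover it. This stands as a limit on how settled the omission is. It makes the fix cheap, but nothing commits anyone to add the item, and measures may also be removed.

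**Other tobacco is captured elsewhere.** The bupropion screening in Section III asks about other tobacco in the past 30 days, and the weekly surveys may record it. The first covers only those requesting that drug, at entry. The second is not described for month 6.

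**NRT.** Because NRT is offered to both arms, a reader might infer that it undermines month-6 cotinine as much as smokeless tobacco does. The documents do not support that: study pharmacotherapy ends at week 12 and unused supply goes back to the clinic. Only outside or unreturned NRT could matter at month 6, and a Pharmacotherapy Use row that ends at week 12 is coherent.

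**Already-abstinent entrants.** A reader might infer that they cannot be identified. Week 1 already schedules the 7-day verified status, cigarettes per day, length of the most recent quit attempt and saliva. These can largely support a sensitivity analysis without such entrants.

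**The illustration.** Five in one arm and none in the other is a strong assumption: 5 of 23 I-FV quitters is 22%. The documents give no reason to expect it in either direction, which is why both directions and the equal case are shown.

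**Conclusion.** The point holds for smokeless and other recreational tobacco and should be fixed. As written, cigarette quitters who use such tobacco are scored as smokers and cannot be separated at month 6, and the promised secondary analysis lacks month-6 data. Confidence is medium, because the schedule is preliminary and survey wording is not shown.

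The size is unknown, since the documents give no share of other-tobacco users. With equal use in both arms the comparison changes little (p=0.009 against 0.005 in the illustration). With unequal use, a handful of participants could move the result either way (p=0.052 or p=0.0006). It would go too far to conclude that the primary result is biased. The documents show only that such bias could not be examined.

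NRT at month 6 is a lesser matter. The two smoker definitions are a minor one: they disagree and both allow some loss of power, without inflating type I error.

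**What to change.** 1. Add rows to the schedule of assessments, linked to the study number described under Data Management: past-7-day use of smokeless and other recreational tobacco at baseline, week 12 and month 6, and one past-7-day NRT question at month 6.
2. Keep the cotinine-verified result in all randomised participants as primary. Add a sensitivity analysis that accepts self-reported cigarette abstinence in those reporting other nicotine use. Read the week-12 comparison alongside reported NRT use.
3. Minor: reconcile the smoker definitions in Section IV and in Eligibility Requirements. Use the scheduled Week 1 items for a sensitivity analysis without entrants who were already 7-day abstinent.
4. Minor: the Design Overview names continuous abstinence as the primary outcome. Reconcile it with the 7-day endpoint used elsewhere.

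The cost is a few survey items and two sensitivity analyses; enrolment stays at 300. The analyses may sit in the SAP, but the items must be in the protocol's schedule. The new items are unverified self-report, so they should inform only the sensitivity analyses.

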Over the past 8 years, we developed a culturally-tailored, in-person, group-based adult smoking cessation program (All Nations Breath of Life – ANBL) using community-based participatory research methods. It takes into account the sacred role of tobacco among many American Indians and how culture affects smoking cessation among AIs. Preliminary data from our recent studies indicate that the internet may be more favorable and appropriate method for reaching younger and more mobile tribal college populations. Web interactivity, immediacy of feedback, and wider reach and accessibility will, we believe, contribute to greater success of the intervention. This proposal is an extension of our previous work. In this study, we will adapt and test a culturally tailored internet-based smoking cessation (**I-ANBL**) program based on ANBL, for a unique subset of the AI population: students enrolled in tribal colleges/universities.

**Primary Aim:** To test the effectiveness of a culturally-tailored internet-based smoking cessation intervention (**I-ANBL**) compared to an internet-based heart healthy diet (I-FV: fruit/vegetable) control condition in a randomized controlled trial with Tribal College students. Our hypothesis is that American Indian tribal college students randomized to the culturally-tailored smoking cessation arm will have significantly higher 7-day point prevalence abstinence (defined as no cigarettes in the past 7 days, biochemically verified) rates at 6 months than those receiving the heart healthy diet intervention.

Secondary Aims	Hypotheses
1. To test the effects of the intervention on intermediate smoking variables including number of cigarettes smoked and number of quit attempts at 6 months following randomization.	1. At 6 months following randomization, among those who continue to smoke, participants in the culturally-tailored (I-ANBL) condition will show a greater reduction in the number of cigarettes smoked than participants in the heart healthy diet arm ( I-FV ).
2. To compare differences between I-ANBL and I-FV in adherence rates to program participation at 6 months following randomization.	2. At 6 months following randomization, participants in the tailored I-ANBL group will have significantly higher adherence rates than smokers in the I-FV group.
Process Objectives	
1. To identify factors that enhance the dissemination aspects of the I-ANBL program.	

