### **Secondary Aims/Hypotheses:**

1. To test the effects of the intervention on intermediate smoking variables including number of cigarettes smoked and number of quit attempts at 6 months following randomization.

Hypothesis 1A: At 6 months following randomization, among those who continue to smoke, participants in the

**I-ANBL** group will show a greater reduction in the number of cigarettes smoked than participants in the **I-FV** group. Mixed models for repeated measures will be used to examine the change in the number of cigarettes smoked over the 6-month study period. To evaluate group differences of reduced cigarette numbers, the models will examine the main effects of time, treatment, and the number of cigarettes smoked at baseline and their interactions. Estimated means at 6 months, which are adjusted for the baseline cigarette numbers, will be reported and compared between the groups.

Hypothesis 1B: Smokers receiving I-ANBL will make greater number of serious quit attempts than smokers receiving I-FV. We will compare the number of quit attempts between the two groups using Poisson regression for count data. In the Secondary Aim 1 analyses, the dropouts will be handled by multiple imputation as described in Primary Aim.

2. To compare differences between **I-ANBL** and **I-FV** in adherence rates to program participation at 6 months following randomization.

Hypothesis 2: At 6 months following randomization, participants in the I-ANBL group will have significantly higher adherence rates than smokers in the **I-FV** group.

We will summarize and compare the measures of program exposure and dose between the groups by descriptive statistics and the *t*-test or chi-square test. Then, we will examine group differences in adherence rates by modeling the binary outcome (dropouts vs. completers) with logistic regression.

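### Number of quit attempts at 6 months is a secondary outcome with its own hypothesis (1B), but the preliminary schedule collects quit attempts only at week 1

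*Protocol*

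**What the plan says.** Secondary Aim 1, in section I and again under Secondary Aims/Hypotheses, concerns "number of cigarettes smoked and number of quit attempts at 6 months following randomization". The Design Overview in section V also lists quit attempts among the secondary endpoints, without a time point. Under Secondary Aims/Hypotheses the aim gets its own hypothesis, 1B: "Smokers receiving I-ANBL will make greater number of serious quit attempts than smokers receiving I-FV". The analysis is stated as well: "We will compare the number of quit attempts between the two groups using Poisson regression for count data". For missing data, "In the Secondary Aim 1 analyses, the dropouts will be handled by multiple imputation as described in Primary Aim".

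The Schedule of Assessments under Measures has one row that names quit attempts: "Quitting history (length of most recent quit attempt, number of quit attempts in the past year"). Its only mark is in the week 1 column. The schedule is introduced as provisional ("The table below represents our preliminary listing of outcome assessments"), and in year one the team will work with community partners to "refine all measures and potentially add or subtract some of them".

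**The concern.** Poisson regression needs a count for each participant over a period after randomisation. A past-year count taken at week 1 covers, in effect, the year before the intervention. It can serve as a baseline covariate, but it cannot show an effect of treatment.

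If the schedule is used as it stands, a stated secondary hypothesis has no specified outcome. The loss would be permanent: an analysis plan written later can define how to use responses, but it cannot create responses that nobody was asked for.

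**Working it through.** The protocol gives no figure to reproduce here. The check sets the outcome beside everything the protocol schedules or describes collecting.

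**What the analysis needs.** A count of quit attempts per participant, from randomisation to month 6. Hypothesis 1B itself gives no time point; the 6 months comes from the aim directly above it.

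**What the schedule collects.** The table has 10 columns (weeks 1 to 8, week 12, 6 months) and 26 measure rows.

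- Quitting history is marked in 1 of 10 columns, week 1.
- At week 12, 22 of the 26 rows are marked. The four unmarked are demographics, smoking history, quitting history and craving: 26 − 4 = 22.
- At 6 months, 18 rows are marked. The same four are unmarked, plus pharmacotherapy use and satisfaction with topics, with educational materials and with cultural appropriateness: 26 − 8 = 18.

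These totals do not measure the size of the problem. They show that survey points already exist after randomisation and that the quit-attempt item is at neither of them.

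**Whether another source supplies the count.**

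- *Cigarettes per day.* The row "Self-reported Smoking status (number of cigarettes/day") is marked in all 10 columns. It records consumption. No row is marked between week 12 and 6 months, so an attempt begun and abandoned in that interval leaves no trace in it.
- *Weekly surveys in Internet Sessions 2-8.* These ask about tobacco use during the week. Quit attempts are not mentioned, and the surveys belong to the session period.
- *6-Month Follow-Up.* This session asks for smoking status and a saliva sample. Quit attempts are not mentioned.
- *Time-to-relapse analysis under Primary Aim/Hypotheses.* This uses 6-month self-report on smoking status. Timeline follow-back is named only in saying that no preliminary relapse estimates exist from it. It has no row in the schedule and is not linked to quit attempts.
- *Survey after the 6-month follow-up (Process Measures and Evaluation).* This covers program exposure and dose, ratings and acceptability.

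None of these is said to yield a quit-attempt count.

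**Whether imputation helps.** Multiple imputation estimates the outcomes of dropouts from participants whose outcome was observed. If no completer has the count, there is nothing to estimate it from.

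**Whether repeating the existing item would help.** Asked at month 6, a 12-month window reaches back 12 − 6 = 6 months before randomisation. That is 6/12 = 50% of the window. The answer would mix attempts before and after randomisation with no means of separating them.

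**The case against.** The strongest reply is that the schedule is expressly preliminary and can be changed in year one, before recruitment begins in year 2 (Implementation Plan). That stands, and it makes the harm conditional on the listing being adopted unchanged. It does not close the gap, because nothing in the text identifies this item as one to add.

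A second reply is that a count might be derived. Cigarettes per day is reported at every scheduled point, and an analysis of time to relapse implies some dated recall of smoking. A derivation rule could properly be left to an analysis plan. This has some force: a partial count for the session weeks may be possible. It still depends on data the protocol does not say it will collect, and for the interval from week 12 to month 6 the schedule offers nothing to work from. Deriving an outcome can be left to an analysis plan; collecting the data for it cannot.

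A third reply is that the point is narrow. That is also true. Section I pairs Secondary Aim 1 only with a hypothesis on cigarette reduction; the quit-attempt hypothesis and its model appear only under Secondary Aims/Hypotheses.

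**Conclusion.** The concern holds. The protocol commits to a secondary outcome and a model for it, and its schedule contains no measurement of that outcome after randomisation. One of the three secondary hypotheses (1A, 1B and 2) is affected; the primary endpoint is not.

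The omission from the schedule is certain on the text. The consequence, that Hypothesis 1B could not be tested as planned, rests on two assumptions: that the preliminary schedule is used without adding the item, and that no unstated source, such as a full timeline follow-back, is collected. It should be corrected while the measures are still open, because the data cannot be recovered after follow-up.

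**What to change.** When the measures are refined in year one:

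1. **Add a quit-attempt count to the schedule at week 12 and month 6.** Let the month-6 window start at randomisation. Every respondent then has the same window, including those who missed week 12, at the price of longer recall. A window starting at the previous assessment shortens recall, but it leaves the total incomplete when week 12 is missed.
2. **Do not reuse the past-year wording after baseline.** Keep the week 1 item; its count can enter the model as a covariate.
3. **Define a serious quit attempt.** Hypothesis 1B uses the term and the protocol does not define it. Apply one counting rule in both arms, and let it say whether the quit date set for all participants at session 2 counts as an attempt.
4. **Name the analysed outcome under Secondary Aims/Hypotheses:** the total count from randomisation to month 6.

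The cost is one web-survey item at two existing survey points and a sentence or two in the Measures and analysis sections. No visit or participant is added. There will be some recall error over the longer window. The community partners have the final say on measures, so the item needs their agreement.
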